### 3. OBJECTIVES AND ENDPOINTS

Objectives	Endpoints
Primary Safety	

 
• To assess the safety and tolerability of rMenB+OMV NZ, PCV13 and other RIV when administered concomitantly to healthy infants at 2, 4, 6 and 12 months of age, throughout the study duration.
 
	
 
• The percentages of subjects with solicited local Adverse events (AEs) (administration site events) and systemic AEs during the 7 days (including the day of vaccination) after the 1st, the 2nd, the 3rd and the 4th vaccination (Visits 1, 2, 3 and 5).
 
• The percentages of subjects with solicited systemic AEs of parotid/salivary gland swelling, fever and rash during the 30 days (including the day of vaccination) after the 4th vaccination (Visit 5).
 
• The percentages of subjects with all unsolicited AEs (including SAEs, AEs leading to withdrawal, AESIs, and medically attended AEs) during 30 days (including the day of vaccination) after the 1st, the 2nd, the 3rd and the 4th vaccination (Visits 1, 2, 3 and 5).
 
• The percentages of subjects with SAEs, AEs leading to withdrawal, AESIs and medically attended AEs from study Day 1 (Visit 1) until study end (6 months or 12 months after last study vaccination, Visit 7).
 

Co-Primary Immunogenicity	

 
• To demonstrate the sufficiency of the immune response to rMenB+OMV NZ when administered concomitantly with PCV13 and other RIV to healthy infants at 2, 4 and 6 months of age, at one month after the 3rd vaccination.
 
 
Criteria: The sufficiency of the immune response to rMenB+OMV NZ at one month after the 3rd vaccination will be demonstrated if the adjusted lower confidence limit for the percentage of subjects achieving serum bactericidal assay using human complement (hSBA) titers <math>\geq</math> Lower Limit of Quantitation (LLOQ) is <math>\geq</math> 60% for the N. meningitidis serogroup B test strains M14459, 96217, NZ98/254 and M13520 (individually); and is <math>\geq</math> 50% for all strains combined (composite endpoint).
	
 
• At 1 month after the 3rd vaccination (Day 151):           
 
– the percentages of subjects with hSBA titers <math>\geq</math>LLOQ; for each of the M14459, 96217, NZ98/254 and M13520 test strains.
 
– the percentages of subjects with hSBA titers <math>\geq</math>LLOQ for all strains combined (composite endpoint).
 
 
 

## CONFIDENTIAL

205239 (MENB REC 2ND GEN-023 (V72\_57))

Objectives	Endpoints

 
To demonstrate the sufficiency of the immune response to rMenB+OMV NZ when administered concomitantly with PCV13 and other RIV to healthy infants at 2, 4, 6 and 12 months of age, at one month after the 4th vaccination.
 
 
Criteria: The sufficiency of the immune response to rMenB+OMV NZ will be demonstrated if the adjusted lower confidence limit for the percentage of subjects with hSBA titers <math>\geq 8</math> (for strains M14459, NZ98/254, M13520) and <math>\geq 16</math> (for strain 96217) is <math>\geq 75\%</math> for the individual N. meningitidis serogroup B test strains and is <math>\geq 65\%</math> for all strains combined (composite endpoint).
	
 
At 1 month after the 4th vaccination (Day 331): 
 
the percentages of subjects with hSBA titers <math>\geq 8</math> (for strains M14459, NZ98/254, M13520) and <math>\geq 16</math> (for strain 96217) for each of the test strains.
 
the percentages of subjects with hSBA titers <math>\geq 8</math> (for strains M14459, NZ98/254, M13520) and <math>\geq 16</math> (for strain 96217) for all strains combined (composite endpoint).
 
 
 

 
To demonstrate the immunological non-inferiority of PCV13 when administered concomitantly with rMenB+OMV NZ and other RIV to healthy infants 2, 4 and 6 months of age, compared to PCV13 without rMenB+OMV NZ, at one month after the 3rd vaccination.
 
 
Criterion: The immunological non-inferiority of PCV13 will be demonstrated if the adjusted lower confidence limit for the between-group ratio of electrochemiluminescence (ECL) assay GMCs is <math>>0.5</math> for each of the 13 PCV13 antigens.
	
 
At 1 month after the 3rd vaccination (Day 151): 
 
the ECL GMCs for each of the 13 PCV13 antigens.
 
 
 

Secondary Immunogenicity	

 
To demonstrate the immunological non-inferiority of PCV13 when administered concomitantly with rMenB+OMV NZ and other RIV to healthy infants 2, 4, 6 and 12 months of age, compared to PCV13 and other RIV alone, at one month after the 4th vaccination.
 
 
Criterion: The immunological non-inferiority of PCV13 will be demonstrated if the lower limit of 2-sided 95% CI for the between-group-ratio of ECL assay GMCs is <math>>0.5</math> for each of the 13 PCV13 antigens.
	
 
At one month after the 4th vaccination (Day 331): 
 
The ECL GMCs for each of the 13 PCV13 antigens.
 
 
 

 
To demonstrate the immunological non-inferiority of PCV13 when administered concomitantly with rMenB+OMV NZ and other RIV to healthy infants at 2, 4, 6 and 12 months of age compared to PCV13 and other RIV alone, at both one month after the 3rd and the 4th vaccinations.
 
 
Criterion: The immunological non-inferiority of PCV13 will be demonstrated if the lower limit of the 2-sided 95% CI for the group differences in percentage of subjects with IgG <math>\geq 0.35</math> <math>\mu</math>g/mL is <math>>-10\%</math> for each of the 13 PCV13 antigens at one month after both 3rd and 4th vaccination.
	
 
At 1 month after the 3rd (Day 151) and the 4th vaccination (Day 331): 
 
Percentages of subjects with serum pneumococcal anti-capsular polysaccharide IgG <math>\geq 0.35</math> <math>\mu</math>g/mL for each of the 13 PCV13 antigens.
 
 
 


 
To demonstrate the immunological non-inferiority of DTaP-HBV-IPV and Hib vaccines when administered concomitantly with rMenB+OMV NZ and PCV13 to healthy infants at 2, 4, and 6 months compared to DTaP-HBV-IPV and Hib vaccines concomitantly administered with PCV13 without rMenB+OMV NZ, in terms of D, T, PT,
 
	
 
At 1 month after the 3rd vaccination (Day 151): 
 
GMCs against the 3 pertussis antigens (Pertussis toxin [PT], pertactin [PRN], filamentous hemagglutinin [FHA]).
 
Percentages of subjects with anti-HBs antibody concentrations <math>\geq 10</math> mIU/mL.
 
 
 

## CONFIDENTIAL

205239 (MENB REC 2ND GEN-023 (V72\_57))

Objectives	Endpoints

FHA, PRN, Hep B and Hib, at one month after the 3rd vaccination.
 
Criterion: The immunological non-inferiority will be demonstrated if the lower limit of the 2-sided 95% CI for the between-group differences is greater than the pre-specified margin† for each antigen at one month after 3rd vaccination.
	
 
– Percentages of subjects with anti-diphtheria and anti-tetanus concentrations <math>\geq 0.1</math> IU/mL.
 
– Percentages of subjects with anti-PRP concentration <math>\geq 0.15</math> <math>\mu</math>g/mL and <math>\geq 1</math> <math>\mu</math>g/mL.
 

 
• To demonstrate the immunological non-inferiority of MMR and VV vaccines when administered concomitantly with rMenB+OMV NZ and PCV13 to healthy subjects at 12 months compared to MMR and VV vaccines concomitantly administered with PCV13, without rMenB+OMV NZ, at one month after vaccination.
 
 
Criterion: The immunological non-inferiority will be demonstrated if the lower limit of the 2-sided 95% CI for the between-group ratio of GMCs is <math>>0.67</math> at one month after the MMR and VV vaccinations.
	
 
• At 1 month after the 4th vaccination (Day 331): 
 
– GMCs against measles, mumps, rubella and VZV antigens.
 
 
 


 
• To evaluate the immune response to rMenB+OMV NZ when administered concomitantly with PCV13 and other RIV to healthy infants at 2, 4, 6 and 12 months of age, at one month after the 3rd vaccination, at 6 months after the 3rd vaccination (immediately before the 4th vaccination), and at one month after the 4th vaccination against the M14459, 96217, NZ98/254 and M13520 test strains.
 
	
 
• At 1 month after the 3rd vaccination (Day 151) 
 
– the percentages of subjects with hSBA titers <math>\geq 5</math>, <math>\geq 8</math> and <math>\geq 16</math> for each of the M14459, 96217, NZ98/254 and M13520 test strains.
 
– the hSBA geometric mean titers (GMTs) against each strain.
 
 
 
• At 6 months after the 3rd vaccination (Day 301, immediately before the 4th vaccination): 
 
– the percentages of subjects with hSBA titers <math>\geq</math>LLOQ for each of the M14459, 96217, NZ98/254 and M13520 test strains.
 
– the percentages of subjects with hSBA titers <math>\geq 5</math> and <math>\geq 8</math> for each of the M14459, 96217, NZ98/254 and M13520 test strains.
 
– the hSBA GMTs against each strain.
 
 
 
• At 1 month after the 4th vaccination (Day 331): 
 
– the percentages of subjects with hSBA titers <math>\geq</math>LLOQ for each of the M14459, 96217, NZ98/254 and M13520 test strains.
 
– the percentages of subjects with hSBA titers <math>\geq 5</math> for each of the M14459, 96217, NZ98/254 and M13520 test strains.
 
– the hSBA GMTs and geometric mean ratios (GMRs) over pre-4th vaccination against each strain.
 
– the percentages of subjects with 4-fold rise* in hSBA titers (from pre-4th vaccination) for each of the M14459, 96217, NZ98/254 and M13520 test strains.
 
 
 

Objectives	Endpoints

 
To evaluate immune responses to routine infant vaccines DTaP-HBV-IPV, Hib, MMR and VV vaccines when administered concomitantly with rMenB+OMV NZ and PCV13 to healthy infants at 2, 4, 6 and 12 months of age, at one month after the 3rd vaccination, at 1 month after the 4th vaccination.
 
	
 
At 1 month after the 3rd vaccination (Day 151): 
 
Percentages of subjects with anti-HBs antibody concentrations <math>\geq 100</math> mIU/mL.
 
Anti-HBsAg GMCs.
 
Percentages of subjects with anti-diphtheria and anti-tetanus concentrations <math>\geq 1</math> IU/mL.
 
Anti-diphtheria and anti-tetanus antibody GMCs.
 
Percentage of subjects with anti-polio type 1, 2 and 3 neutralization antibody titers <math>\geq 8</math>.
 
 
 
At 1 month after the 4th vaccination (Day 331): 
 
Seroresponse, defined as post-vaccination anti-VZV virus, anti-measles virus, anti-mumps virus and anti-rubella virus antibody concentration <math>\geq</math> a protective threshold† among subjects who were seronegative (antibody concentration <math><</math> assay cut-off) before vaccination.
 
 
 

\* A 4-fold rise in hSBA titers is defined as

- if pre-vaccination titer  $<$  Limit of Detection (LOD), then a post-vaccination titer  $\geq 4$  times the LOD or  $\geq$  LLOQ, whichever is greater;

- if pre-vaccination titer is  $\geq$  LOD but  $<$  LLOQ, then a post-vaccination titer  $\geq 4$  times the LLOQ;

- if pre-vaccination titer is  $\geq$  LLOQ, then a post-vaccination titer  $\geq 4$  times the pre-vaccination titer, where pre-vaccination titer=pre-4th dose titers (Day 301)

† The endpoints and thresholds used for evaluation of the non-inferiority criteria for DTaP-HBV-IPV and Hib vaccines can be found in Protocol Amendment 8 Table 21 and the thresholds and endpoints for evaluating the non-inferiority criteria for MMR and VV vaccines can be found in Protocol Amendment 8 Table 22.

‡ Protective thresholds for analyses of anti-VZV virus, anti-VZV, anti-measles virus, anti-mumps virus and anti-rubella virus antibody concentrations are present in Section 5.3.2.

§ Visit 7 will occur either on Day 481 (for subjects who have not yet reached the 6-month follow-up after the last dose at the time protocol amendment 7 took effect) or on Day 661 (for all other subjects).

Note 1: In the context of this study, the following are considered as RIVs at different visits:

Visit 1 and Visit 2: DTPa-HBV-IPV, HRV, Hib;

Visit 3: DTPa-HBV-IPV, Hib;

Visit 5: MMR and VV.

## 4. ANALYSIS SETS

### 4.1. Definition

#### 4.1.1. Enrolled Set

All screened subjects who provide informed consent and provide demographic and/or baseline screening assessments and are randomized and have received a Subject ID, regardless of the subject's treatment status in the study.

**4.1.2. Exposed Set**

All subjects in the Enrolled Set who receive a study vaccination.

**4.1.3. Safety Set****4.1.3.1. Solicited Safety Set (solicited local and systemic adverse events and other solicited adverse events)**

All subjects in the Exposed Set with any solicited adverse event data.

**4.1.3.2. Unsolicited Safety Set (unsolicited adverse events)**

All subjects in the Exposed Set with unsolicited adverse event data.

**4.1.4. Full Analysis Set (FAS) for Immunogenicity**

All subjects in the Exposed Set who provide immunogenicity data at either one month after their 4th vaccination or one month after their 3rd vaccination for at least 1 antigen/strain.

In case of vaccination error, subjects in the FAS sets will be analysed “as randomized” (i.e., according to the vaccine a subject was designated to receive, which may be different from the vaccine the subject actually received).

**4.1.5. Per Protocol (PP) Set for Immunogenicity**

All subjects in the FAS Immunogenicity who:

- Correctly receive the vaccine (i.e., receive the vaccine to which the subjects are randomized and at the scheduled time points).
- Have no protocol deviations leading to exclusion in at least one timepoint of analyses for immunogenicity.
- Are not excluded due to other reasons defined prior to unblinding or analysis.

Examples for subjects excluded due to other reasons than protocol deviations are:

- Subjects who withdrew informed consent.

Examples for subjects excluded due to protocol deviations are:

- Subjects who did not receive all the study vaccines up to Dose 3 for primary 3 doses analyses or up to Dose 4 for the 4th dose analyses.
- who received a vaccine not specified or forbidden in the protocol up to Visit 4 for primary 3 doses or up to Visit 6 for the 4th dose.

- who received a medication/product leading to exclusion from a per-protocol analysis as listed in Protocol Section 6.7.2 up to Visit 4 for primary 3 doses or up to Visit 6 for the 4th dose.
- who presented a medical condition leading to exclusion from a per-protocol analysis as listed in Protocol Section 6.8 up to Visit 4 for primary 3 doses or up to Visit 6 for the 4th dose.
- who did not comply with the post Dose 3 (for primary 3 doses) or pre and post Dose 4 (for the 4th dose) blood sample schedule, i.e. 21 to 60 days post the vaccination.
- who had no immunogenicity results post Dose 3 (for primary 3 doses) or post Dose 4 (for the 4th dose).

The allowed intervals between each study visit are given in [Table 5](#). Subjects will not be eligible for inclusion in the per-protocol cohort for analysis of primary 3 doses if study visits are performed outside this interval up to visit 4, and they will not be eligible for analysis of the 4th dose if the study visit is performed outside this interval up to Visit 6.

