8. Subjects who terminate the study early are recommended to complete certain study-related procedures. See Section 5.6.15 for further details.
9. Solicited AEs that are ongoing after the 7-day reporting period will continue to be recorded in the eDiary until resolution or day 30, whichever occurs first.
10. For subjects who have not yet reached the 6-month safety follow-up after the last dose at the time protocol amendment 7 takes effect, Visit 7 will occur on Day 481.
11. Visit 7 may be a telephone contact during special circumstances. Refer to Section 5.6.15 for study procedures to be considered during special circumstances.
12. COVID-19 infection related AEs and SAEs should be recorded in a separate eCRF.

¹³ ***Either PCV13 or PCV20 is allowed to be given at 12 months of age (Visit 5) for subjects who have not reached Visit 5 at the time the protocol amendment 8 becomes effective.***

The investigator should arrange study visits within the interval described in [Table 6](#).

Table 6 Intervals Between Study Visits

Interval	Optimal length of interval	Allowed interval ^{1,2}
Visit 1 → Visit 2	60 days	29 days – 81 days
Visit 2 → Visit 3	60 days	29 days – 81 days
Visit 3 → Visit 4	30 days	21 days – 60 days
Visit 3 → Visit 5	180 days	173 days – 201 days
Visit 5 → Visit 6	30 days	21 days – 60 days
Visit 5 → Visit 7 (Study termination) ³	180 days	173 days – 201 days
Visit 5 → Visit 7 (Study termination)	360 days	353 days – 381 days

¹The investigator should arrange study visits within this interval as subjects may not be eligible for inclusion in the PPS cohorts if they make the study visit outside this interval. All visits and windows should be planned using the day of last vaccination as the reference point

²The allowed interval have been modified in keeping with ACIP guidelines to facilitate the safe scheduling of study visits during the COVID-19 pandemic situation.

³ For subjects who have not yet reached the 6-month safety follow-up after the last dose at the time protocol amendment 7 takes effect, Visit 7 will occur on Day 481.

Refer to [Table 6](#) for intervals between study visits that determine subjects' eligibility for inclusion in the per-protocol analysis.

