5.6.11.1. Blood sampling for immune response assessments

Blood samples will be obtained from each enrolled subject in both study groups at 3 study visits as follows:

- Visit 4 at Day 151, i.e., 30 (-9 to +30) days after the 3rd vaccination.
- Visit 5 at Day 301, i.e., 180 (-7 to +91) days after the 3rd vaccination (pre-4th vaccination).
- Visit 6 at Day 331 i.e., 30 (-9 to +30) days after the 4th vaccination.

In order to support all serological assay testing, a volume of approximately 5 mL of whole blood (to provide approximately 2 mL of serum) should be drawn from each subject at each pre-defined timepoint mentioned above, resulting in a total of approximately 15 mL over the entire study period. After centrifugation, serum samples should be kept at -20°C/ -4°F or below until shipment. Refer to the SPM and Central Laboratory Investigator Manual for more details on sample storage conditions.

A topical anesthetic (e.g. EMLA adhesives or cream) may be used at the site of blood sample draw, according to local practice, in order to minimize pain.

The blood will be used for immunological assays, as described in Section [5.7.4](#).

In clinic visits where a blood draw and a vaccination are planned, ensure all serology samples are taken **prior** to vaccination. The following are clinical circumstances that warrant delay of blood samples collection for immunogenicity assessments in this study:

- Receipt of systemic antibiotics within the previous 3 days (72 hours) before blood sample collection

In the event that a subject meets the criterion for delay of blood samples collection, blood samples collection may proceed once the appropriate window for delay has passed.

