9.2.5. Per Protocol (PP) Set for Immunogenicity

All subjects in the FAS Immunogenicity who:

- Correctly receive the vaccine (i.e., receive the vaccine to which the subjects is randomized and at the scheduled time points).
- Have no protocol deviations leading to exclusion as defined prior to unblinding / analysis.
- Are not excluded due to other reasons defined prior to unblinding or analysis

Examples for subjects excluded due to other reasons than protocol deviations are:

- Subjects who withdrew informed consent.
- Subjects who did not receive all the study vaccines up to Dose 3 for primary 3 doses analyses or up to Dose 4 for the 4th dose analyses;
- who received a vaccine not specified or forbidden in the protocol up to Visit 4 for primary 3 doses or up to Visit 6 for the 4th dose;
- who received a medication/product leading to exclusion from a per-protocol analysis as listed in Section 6.7.2 up to Visit 4 for primary 3 doses or up to Visit 6 for the 4th dose.

- who presented a medical condition leading to exclusion from a per-protocol analysis as listed in Section 6.8 up to Visit 4 for primary 3 doses or up to Visit 6 for the 4th dose.
- who did not comply with the post Dose 3 (for primary 3 doses) or post Dose 4 (for the 4th dose) blood sample schedule (Table 6).
- who had no immunogenicity results post Dose 3 (for primary 3 doses) or post Dose 4 (for the 4th dose).

The allowed intervals between each study visit are given in Table 6. Subjects will not be eligible for inclusion in the per-protocol cohort for analysis of primary 3 doses if the study visit is performed outside this interval up to visit 4, and they will not be eligible for analysis of the 4th dose if the study visit is performed outside this interval up to Visit 6.

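### The fourth-dose per-protocol set has no single rule: SAP 4.1.5 sets a sampling window that a pre-Dose-4 sample cannot meet, and protocol Table 6 ends the Visit 5 interval at 201 days where every other text gives 271

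*SAP*

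**What the plan says.** **Sampling bullet.** Protocol 9.2.5 gives as an exclusion those "who did not comply with the post Dose 3 (for primary 3 doses) or post Dose 4 (for the 4th dose) blood sample schedule", with a pointer to Table 6. SAP 4.1.5 rewords this to those "who did not comply with the post Dose 3 (for primary 3 doses) or pre and post Dose 4" and closes the bullet with "blood sample schedule, i.e. 21 to 60 days post the vaccination". That is the only window in the bullet. SAP Section 8 lists a different change to the per-protocol definition (free of deviations in at least one timepoint) and does not mention this one.

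**Visit 3 to Visit 5 interval.** Protocol Table 6 (Section 5.5) gives "173 days – 201 days", and the sentence beneath it makes the table decisive for "eligibility for inclusion in the per-protocol analysis". Protocol 9.2.5 then says of subjects that "they will not be eligible for analysis of the 4th dose if the study visit is performed outside this interval up to Visit 6". Elsewhere the protocol is wider: Section 5.6.11.1 has "Visit 5 at Day 301, i.e., 180 (-7 to +91) days after the 3rd vaccination (pre-4th vaccination", and the synopsis, Section 3 and the visit-window row of Table 5 carry the same -7/+91. SAP Section 2 repeats -7/+91 and SAP Table 5 gives 173 to 271 days. The last paragraph of SAP 4.1.5 ("The allowed intervals between each study visit are given in" Table 5) imposes the same bar on out-of-interval visits, with 271 as the limit. SAP Section 1 records that the SAP is written to Protocol Amendment 8.

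**The concern.** SAP 5.3.1 makes the per-protocol set the primary population for the primary and secondary immunogenicity analyses. For the fourth dose that covers the Family 2 co-primary sufficiency objective and the post-Dose-4 PCV and MMR/varicella non-inferiority comparisons.

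Read literally, the SAP bullet removes every infant from the fourth-dose set. Read charitably, it still leaves a question: does a missing or mistimed Visit 5 sample remove an infant from the fourth-dose analysis? The Family 2 endpoints use only the post-Dose-4 titre, so there is no reason for it to do so.

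The interval conflict is more concrete, because the two documents classify the same infant differently. The full-analysis-set repeat is not a complete check. SAP 4.2.4.3 applies the visit-level codes for out-of-window vaccination (2080.X) and sampling (2090.X) to the full analysis set as well, and Visit 5 is also the Dose 4 visit.

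**Working it through.** **1. Can a pre-Dose-4 sample meet the SAP bullet?**
- Relative to Dose 3, the Visit 5 window is 180 - 7 = 173 to 180 + 91 = 271 days. The bullet's window ends at day 60. The gap is 173 - 60 = 113 days, so there is no overlap.
- Relative to Dose 4, the sample is taken before vaccination, at day 0 or earlier. That is also outside 21 to 60.
- The window fits the other two samples: Visits 4 and 6 are 30 - 9 = 21 to 30 + 30 = 60 days after Doses 3 and 4.

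**2. Which rows of protocol Table 6 reproduce from the protocol's own windows?**

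| Interval | Window | Result | Table 6 |
|---|---|---|---|
| Visit 3 to 4; Visit 5 to 6 | 30 -9/+30 | 21–60 | 21–60 |
| Visit 5 to 7 (6 months) | 180 -7/+21 | 173–201 | 173–201 |
| Visit 5 to 7 (12 months) | 360 -7/+21 | 353–381 | 353–381 |
| Visit 3 to 5 | 180 -7/+91 | 173–271 | **173–201** |

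Only the Visit 3 to Visit 5 row fails. Its 201 equals 180 + 21, the value in the 6-month Visit 7 row.

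**3. Size of the disputed range.**
- Permitted under -7/+91: 271 - 173 + 1 = 99 days.
- Permitted under Table 6: 201 - 173 + 1 = 29 days.
- In dispute: 271 - 202 + 1 = 70 days. With Dose 3 on Day 121 these are study Days 121 + 202 = 323 to 121 + 271 = 392.

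**4. Illustrative power if the narrower limit removed infants.** The documents do not say how many infants were seen on those days, so the loss rates below are assumptions.

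*Post-Dose-4 composite.* The response probability per strain is Φ[(mean log10 titre - log10 cut-off)/SD], with means from protocol Table 19 and SDs from Table 18:
- M14459: (1.53148 - log10 8)/0.45097 gives 0.918
- 96217: (3.06183 - log10 16)/0.63454 gives 0.998
- NZ98/254: (1.57978 - log10 8)/0.53796 gives 0.896
- M13520: (1.41225 - log10 8)/0.36477 gives 0.919

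Under independence, as protocol 9.1 assumes, the product of the unrounded values is 0.7543. Power is the binomial probability that the Clopper-Pearson lower limit (two-sided alpha 0.0333) is at least 0.65.

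*Measles and varicella GMC ratio.* With ratio 0.9, SD 0.45 and margin 1/1.5, the noncentrality is [log10 0.9 - log10(1/1.5)]/[0.45·√(1/n1 + 1/n2)]. At 480/240 this is 0.1303/0.03558 = 3.66. Power comes from the noncentral t distribution against the 97.5% point. The 480/240 result matches the 95.5% in protocol Table 22.

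| Assumed further loss, both arms | n1/n2 | Composite power | Measles/varicella power |
|---|---|---|---|
| 0% | 480/240 | 99.8% | 95.5% |
| 10% | 432/216 | 99.5% | 93.5% |
| 20% | 384/192 | 99.1% | 90.5% |
| 30% | 336/168 | 97.7% | 86.4% |

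The 480 and 240 are already net of a 40% drop-out allowance (800 × 0.6 and 400 × 0.6). If that allowance covers out-of-window visits, the 0% row applies. The 99.8% baseline is lower than the >99.999% for this objective in protocol Table 17, which these inputs give only at about n = 800 (0.99999).

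**The case against.** *The SAP bullet is a misplaced modifier in a list of examples.* The 21 to 60 days plainly describes the post-dose samples, SAP Table 5 gives Visit 5 its own interval, and nobody would program a rule that empties the set. That is probably right about intent. It does not make the written rule correct, and it does not settle what a missing or mistimed Visit 5 sample does.

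*The SAP already handles sample problems by visit.* Codes 2090.X and 2100.X censor a single visit, and the revised definition keeps anyone free of deviations at one timepoint or more. This stands in part: part of the fix restates existing machinery. But SAP 4.2.4.1 also lists 2090 and 2100 as codes that exclude the whole subject, and the added words point that way.

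*Protocol 9.2.5 already bars out-of-interval visits up to Visit 6, so the addition changes little.* True for the timing of Visit 5. It does not cover a sample that is missing at an on-time visit.

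*Table 6 is one stray cell and the later SAP is internally consistent.* It is the outlier, and 271 is the likelier intent. But the text under the table makes it decisive for eligibility, and SAP Section 8 does not declare a departure. The case-by-case clause in protocol 5.6.15 covers special circumstances only. Footnote 1 to both tables says such subjects may be ineligible, whereas the text of both definitions says they will not be eligible. Protocol 9.8 defers the explanation of changes to the study report, which comes after the population has been applied.

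*No effect is demonstrated.* This stands: the loss rates are assumed and may be zero, and composite power is 97.7% even in the worst row.

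**Conclusion.** Both defects are in the current text. The SAP sampling rule cannot be met by any pre-Dose-4 sample. The two documents also disagree on whether a Visit 5 on days 202 to 271 after Dose 3 (70 of 99 permitted days) keeps an infant in the fourth-dose per-protocol set. The window arithmetic needs no assumption beyond the stated visit windows.

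The practical effect cannot be sized from the documents. On the assumed losses it is small for the co-primary composite and larger, though still moderate, for measles and varicella. The case for acting rests on having one stated rule for a co-primary population, not on lost power. It should be fixed; the confidence is high.

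**What to change.** 1. In SAP 4.1.5, delete *pre and* from the sampling bullet. If the words are kept, replace the 21-to-60-day clause with a reference to SAP Table 5.
2. State that, when Visit 5 itself is within the allowed interval, a missing pre-Dose-4 sample (2100.X) or one drawn after Dose 4 (2090.X) is censored at Visit 5 only. It then affects only the endpoints that use it: four-fold rise, geometric mean ratio and MMR/varicella seroresponse. Keep the existing rule that a Visit 5 outside the allowed interval excludes the infant from the fourth-dose per-protocol analysis.
3. Correct the Visit 3 to Visit 5 row of protocol Table 6 to 173–271 days, or state in SAP Section 8 that SAP Table 5 governs. The sponsor should confirm that 271 is the intended limit.

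The cost is a few words in the SAP plus either one protocol table cell or one sentence in SAP Section 8. No new data are needed.
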